#### **Number of Subjects (planned):**

Phase 1 dose escalation: up to 36 subjects

Phase 1b dose expansion: up to 60 subjects

Total: approximately 96 subjects

#### **Diagnosis and Main Criteria for Inclusion:**

1. Voluntarily provide signed informed consent after review of verbal and written material about the trial and agree to abide with protocol requirements. All study related activities must be carried out after written consent is obtained.
2. Subjects must be  $\geq 18$  years of age at the time of signing the ICF.
3. Subjects must have an ECOG status of 0 – 2 ([Appendix 3](#)).
4. For **MM**, subjects must have measurable disease by IMWG 2016 criteria ([Kumar, 2016; Appendix 1](#)) as defined by at least one of the following:
  - Serum monoclonal protein (M-protein) concentration  $\geq 0.5\text{g/dL}$ .
  - Urine M-protein excretion of  $\geq 200\text{mg}$  in 24 hours.
  - Serum free light chain concentration  $\geq 10\text{mg/dL}$  with an abnormal ( $<0.26$  or  $>1.65$ )  $\kappa:\lambda$  free light chain ratio.
5. For **DLBCL**, subjects must have measurable disease by Lugano criteria ([Cheson, 2014; Appendix 2](#)).
6. **MM** subjects who are relapsed/refractory to immune modulator, proteasome inhibitor and anti-CD38 therapy. Subjects who could not tolerate a protease inhibitor (PI), immunomodulatory agent (IMiDs), and a CD38-directed cytolytic antibody are eligible to participate and R/R MM subjects who are intolerant of established therapies known to provide clinical benefit in multiple myeloma.
7. **DLBCL** subjects who are relapsed or refractory with at least two prior line including treatment with R-CHOP, R-EPOCH, R-hyperCVAD and other standard of care therapies. Lines of therapy could have been discontinued due to completion of therapy, intolerance, or lack of response.

**Note:** Relapsed disease is defined as progression of disease, after initial response to previous treatment, more than six months after end of treatment. Refractory disease is defined as resistance to treatment due to lack of response or progression of disease during treatment or within six months after end of treatment.

8. For dose expansion cohort 1 and 2 only; subjects must have local t(4;14) test results available for enrollment.
9. At enrollment, subjects should have an estimated life expectancy  $\geq$  3 months in the opinion of the Investigator.
10. Subjects must have sufficient organ and marrow function as defined below:
  - Hemoglobin  $\geq$ 8g/ dL
  - Platelets  $>75 \times 10^9/L$  (includes transfusion dependent subjects)
  - Absolute neutrophil count (ANC)  $\geq 1000/\text{mm}^3$ . Growth factors within 7 days of screening is not allowed to meet ANC eligibility criteria
  - Aspartate aminotransferase (AST) and alanine aminotransferase (ALT)  $<2.5 \times \text{ULN}$ , or if attributed to tumor involvement, AST, and ALT  $<5 \times \text{ULN}$ .
  - Bilirubin  $\leq 1.5 \times \text{ULN}$
  - Creatinine clearance  $\geq 40 \text{ ml/min}$ . Estimated creatinine clearance calculated using the Cockcroft-Gault formula
  - Coagulation parameters: prothrombin time/ international normalized ratio (PT/INR)  $<1.5 \times \text{ULN}$  and activated partial thromboplastin (aPTT)  $< 1.5 \times \text{ULN}$ .
11. Females must not be breastfeeding or pregnant at screening (as documented by a negative beta-human chorionic gonadotropin [ $\beta$ -hCG] test with a minimum sensitivity of 25 IU/L or equivalent units of  $\beta$ -hCG). A separate baseline assessment is required if a negative screening pregnancy test was obtained more than 72 hours before the first dose of study treatment. All female subjects will be considered to be of childbearing potential unless they are postmenopausal (at least 12 months consecutively amenorrheic, in the appropriate age group, and without other known or suspected cause) or have been sterilized surgically (ie, bilateral tubal ligation, total hysterectomy, and/or bilateral oophorectomy, with all surgery completed at least 1 month before the first dosing).
12. Females of childbearing potential must not have had unprotected sexual intercourse within 30 days prior to study entry and must agree to use a highly effective method of contraception, beginning at least 14 days prior to study entry, during treatment cycles, and for 30 days after the final dose of study treatment and have a male partner who uses a condom. Highly effective contraception includes:
  - Placement of an intrauterine device.
  - Established hormonal contraceptive methods: oral, injectable, or implant. Females who are using hormonal contraceptives must have been on a stable dose of the same hormonal contraceptive product while enrolled on trial and must continue to use the same contraceptive during the study and for one months after last dose of study drug.
13. Male subjects must either practice complete abstinence **or** agree to use a latex or synthetic condom, even with a successful vasectomy (medically confirmed azoospermia), during study treatment and for 30 days after the final dose of study treatment.  
**Note:** Male subjects must not donate semen or sperm from the first dose of study treatment, during study treatment (including during dose interruptions), and for 30 days after the final dose of study treatment.

**Diagnosis and Main Criteria for Exclusion:**

1. Subjects with plasma cell leukemia defined as a plasma cell count  $>2000/\text{mm}^3$ .

2. Subjects with Waldenstrom's macroglobulinemia or smoldering MM.
3. Subjects with corrected serum calcium >14mg/dL (>3.5mmol/L) or free ionized calcium >6.5mg/dL (1.6mmol/L).
4. Subjects with known systemic amyloidosis.
5. Subjects who had prior treatment with SETD2 or NSD2 inhibitor.
6. Prior cancer therapy for disease under study within the past 4 weeks or 5 half-lives, whichever is shorter. All prior treatment-related adverse events (AEs) must have resolved to Grade 1 or baseline per NCI CTCAE 5.0.
7. Have known active central nervous system (CNS) or any leptomeningeal metastasis of primary extracranial tumor. Subjects with previously treated brain metastases may participate provided they are stable (without evidence of progression by imaging 4 weeks prior to the first dose of study treatment and any neurologic symptoms have stabilized), have no evidence of new or enlarging brain metastases, and are on stable or tapering doses of steroids for at least 7 days prior to first dose of study treatment.

*Note:* Subjects with asymptomatic brain metastases found on screening magnetic resonance imaging (MRI) may be entered into the study without prior radiation therapy to the brain if they do not require immediate surgical or radiation therapy in the opinion of the treating Investigator and in the opinion of a radiation therapy or neurosurgical consultant.

8. Subjects taking medications that are known as strong and moderate cytochrome P450 3A4 (CYP3A4) and P-gp inducers/inhibitors (including St. John's Wort). Subjects taking ARA, H2 blockers and PPIs. Subjects must stop taking such medications and must not take them for the duration of their participation in the study. Washout of minimum 14 days or 5 half-lives (whichever is longer) prior to starting EZM0414 is required.
9. Subjects unwilling to exclude Seville oranges, grapefruit juice, AND grapefruit from their diet and all foods that contain those fruits from time of enrolment to while on study.
10. Have a known active infection with hepatitis B virus (HBV, as measured by positive hepatitis B surface antigen), hepatitis C virus (HCV, as measured by positive hepatitis C antibody).  
*Exceptions:* Subjects with a history of hepatitis B or C who have normal ALT AND are hepatitis B surface antigen negative and/or have undetectable HCV RNA are eligible.
11. Known to be human immunodeficiency virus (HIV) seropositive.
12. Subjects with active acute or chronic systemic infection requiring systemic treatment, including COVID-19.
13. Has cardiovascular impairment: history of congestive heart failure greater than NYHA Class II, uncontrolled arterial hypertension (ie, systolic blood pressure (BP) >150 mm Hg and/or diastolic BP >110 mm Hg), unstable angina, myocardial infarction, or stroke within 6 months prior to the planned first dose of study drug; or ventricular cardiac arrhythmia requiring medical treatment ([Appendix 4](#)).
14. Prolongation of corrected QT interval using Fridericia's formula (QTcF) to > 480 msec or history of long QT syndrome. A history or evidence of current clinically significant uncontrolled arrhythmias. History of additional risk factors for Torsade de Pointes including heart failure, hypokalemia, family history of Long QT Syndrome, and use of concomitant medications that are known to increase the risk of Torsade de Pointes ([www.crediblemeds.org](http://www.crediblemeds.org)).
15. Known left ventricular ejection fraction (LVEF) < 50% by either echocardiogram (ECHO) or multigated acquisition (MUGA).
16. Prior major surgery within 4 weeks of treatment start.
17. Known hypersensitivity to components of the investigational product.
18. Subjects who have received treatment with any unapproved drug product within 4 weeks prior to screening.

19. Current participation in any other interventional clinical study except for follow-up.
20. Subjects with a history of or active malignancy other than disease under study, except for:
  - Cervical carcinoma Stage 1B or less.
  - Surgically treated non-invasive basal cell and squamous cell skin carcinoma.
  - Malignant melanoma with a complete response for more than 10 years.
  - Curable cancer and/or hematologic malignancies diagnoses with a complete response for more than 5 years.
21. Underlying medical/social conditions that in PI opinion will place the subject in significant risk and affect the interpretation of toxicity and adverse events assessments.
22. Inability to take oral medication or known gastrointestinal (GI) disease, GI procedure or medical condition that could interfere with the oral absorption or tolerance of the study drug.

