### 7.5.2. Dose Reductions and Interruptions

EZM0414 dose adjustments/reductions and interruptions will be allowed. However, an interruption in the administration of EZM0414, for more than **14 days** must be discussed with the Sponsor's or Designee Medical Monitor before treatment can be resumed.

Toxicity will be managed by concomitant medication (as appropriate), treatment interruption, dose reduction, and treatment discontinuation, or a combination of these. During treatment with study drug, dose interruption and reduction for subjects who experience study drug-related toxicity will be in accordance with the Dose Modifications Instructions in [Table 4](#).

For subjects who require dose interruption due to study drug-related toxicity, the treatment may restart once the toxicity has resolved to Grade  $\leq 1$  or baseline according to the Dose Modifications Instructions in [Table 4](#). If clinically appropriate thereafter re-escalation can be considered in consultation with the Sponsor's Medical Monitor.

Based up on physical exam and respiration rate, follow-up examination should be performed as clinically indicated. For continuation of treatment for cycle 2 and beyond, subjects must meet the following retreatment criteria:

- Platelet count must be  $\geq 50 \times 10^9/L$ , include transfusion dependent subjects
- Absolute neutrophil count (ANC) must be  $\geq 1.0 \times 10^9/L$  if no lymphoma infiltration of bone marrow **OR** ANC must be  $\geq 0.75 \times 10^9/L$  with bone marrow infiltration, and
- Any Grade 3 or higher toxicity must have resolved to Grade 1 or baseline, unless otherwise noted.

The suggested dose reductions for the three lowest dose levels are as follows based on the dose reduction increments included in [Table 4](#):

- Starting dose: 100 mg QD EJM0414
  - 1st dose reduction 75 mg
  - 2nd dose reduction: 50 mg
- Step down dose (if needed): 75 mg QD EJM0414: 1st dose reduction 50 mg and 2nd dose reduction: 25 mg
- Starting dose: 200 mg QD EJM0414
  - 1st dose reduction 150 mg
  - 2nd dose reduction: 100 mg
- Starting dose: 300 mg QD EJM0414
  - 1st dose reduction 200 mg
  - 2nd dose reduction: 100 mg

All final decisions on dose reductions in response to drug-related AEs should be made after discussion with the Sponsor's Medical Monitor.

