### 7.5.3. Safety Management Guidelines

#### Investigation: QTcF prolongation

The QTcF is the QT interval corrected for heart rate according Fridericia's formula (QTcF). For eligibility and withdrawal, subjects QTcF value will be used. For purposes of data analysis, QTcF values will be used.

If QTcF >500 msec or QTcF prolongation >60 msec from baseline is observed at any point during the study treatment and confirmed, the below guidance must be followed:

1. Assess the quality of the ECG recording and the QT value and repeat if needed.
2. Interrupt study treatment until confirmed resolution of QTcF and as per dose reduction guidelines in [Table 4](#).
3. Determine the serum electrolyte levels (in particular hypokalemia hypomagnesemia). If abnormal, correct abnormalities before resuming study drug treatment.
4. Review concomitant medication use for other causes for QT prolongation (refer to [qtdrugs.org](http://qtdrugs.org) for known QT prolonging drugs), and for drugs with the potential to increase the risk of drug exposure related QT prolongation (e.g., concomitant use of CYP3A4 inhibitors).
5. Check study drug dosing diary and treatment compliance.
6. Increased ECG safety monitoring is recommended during or in-between subsequent visits.

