## 8. SELECTION AND WITHDRAWAL OF SUBJECTS

To be eligible for inclusion in the trial, the subject has to meet all inclusion criteria and must not violate any of the exclusion criteria. Deviations to the protocol inclusion and exclusion criteria will not be allowed. If there is a question about eligibility, the investigator should consult with the sponsor's medical monitor.

Investigators should ensure that all study enrolment criteria have been met at screening. If a subject's status changes (including laboratory results or receipt of additional medical records) after screening but before the first dose of study drug is given such that they no longer meet all eligibility criteria, he or she should be excluded from participation in the study.

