### 9.3. Concomitant Medications

Unless clinically indicated, subjects should avoid taking additional non-study medications that may interfere with study treatments. Any medication or vaccine, including over-the-counter or prescription medicines, vitamins, and/or herbal supplements that the patient is receiving at the time of enrolment or receives during the study must be recorded in the CRF along with:

- Reason for use
- Dates of administration including start and end dates
- Dosage information including dose and frequency

Details of prohibited medications are detailed in [Table 12](#) and [Appendix 6](#).

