**Table 12: Prohibited Medications**

Unless stated otherwise, these medications are prohibited from the time that subjects enter the main screening period until the last dose of study treatment. The pre-screen may be done whilst on prior therapy.	
Any investigational anti-cancer therapy other than those under investigation in this study	Should not be given concomitantly whilst the patient is on study treatment
Any concurrent chemotherapy, radiotherapy, immunotherapy, biologic or hormonal therapy, or any other novel agent for cancer treatment other than those under investigation in this study	Should not be given concomitantly whilst the patient is on study treatment. Palliative radiotherapy may be used for the treatment of pain, provided the Investigator does not consider these are indicative of clinical progression. Study treatment should be discontinued a minimum of 3 days before a patient undergoes palliative radiotherapy, and study treatment restarted within 4 weeks (provided any bone marrow toxicity has recovered).
Herbal medications and supplements	Should not be given concomitantly unless agreed by the Sponsor. This is due to their potential to modulate CYP3A4 or activity of other enzymes which are not well characterized (see also below), and further details in Appendix 6 .
Concomitant medications known to significantly modulate CYP3A4 activity	The principal enzyme for metabolizing EZM0414 is CYP3A4/5. Subjects should avoid concomitant medications and foods known to significantly modulate CYP3A4/5 activity (potent/moderate inhibitors or inducers of CYP3A4). The required washout period prior to starting study treatment is

	minimum 14 days or 5 half-lives (whichever is longer). See Appendix 6 .
Concomitant medications known to significantly modulate P-gp activity	EZM0414 is also P-gp substrates. Co-administration of P-gp inhibitors or inducers may affect exposure to EZM0414, and it is recommended that these are not co-administered with EZM0414. See Appendix 6 .
Concomitant medications known to significantly alter gastric pH	EZM0414 has pH-dependent solubility. The EZM0414 has potential interact with gastric pH-dependent acid-reducing agents, such as antacids, histamine H2-receptor antagonists (H2 blockers), and proton pump inhibitors (PPIs).
Live virus and bacterial vaccines	Prohibited whilst the patient is receiving study medication and during the 30-day follow-up period.

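### Drugs known to raise Torsade de Pointes risk are barred at entry, but no supplied text restricts starting one on treatment unless another restricted class catches it

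*Protocol*

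**What the plan says.** Exclusion 14, in the Synopsis and again in Protocol Section 8.2, covers QTcF above 480 msec, long QT syndrome, uncontrolled arrhythmia and further Torsade de Pointes risk factors. The last of these is "use of concomitant medications that are known to increase the risk of Torsade de Pointes".

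Protocol Section 8 says how long eligibility applies: a subject is excluded if status changes "after screening but before the first dose of study drug is given such that they no longer meet all eligibility criteria".

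Exclusion 8 is written differently. For CYP3A4 and P-gp modulators and acid-reducing agents it adds that subjects "must not take them for the duration of their participation in the study".

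The on-study rules are these:
- Section 9.3: "Unless clinically indicated, subjects should avoid taking additional non-study medications that may interfere with study treatments".
- Table 12, header: "Unless stated otherwise, these medications are prohibited from the time that subjects enter the main screening period until the last dose of study treatment". Its rows cover other anti-cancer treatment, herbal products, CYP3A4 modulators, P-gp modulators, drugs that alter gastric pH, and live vaccines.
- Section 7.5.2: "For continuation of treatment for cycle 2 and beyond, subjects must meet the following retreatment criteria". The criteria listed are platelets, neutrophils and recovery from toxicity.
- Section 7.5.3: when QTcF exceeds 500 msec, or rises more than 60 msec from baseline, and this "is observed at any point during the study treatment and confirmed, the below guidance must be followed". One step of that guidance is a review of QT-prolonging co-medication.

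**The concern.** The sponsor treats Torsade-risk co-medication as unacceptable before any study drug has been given. Once the subject is taking EZM0414, when the two effects could combine, the restriction lapses. No supplied text gives a reason for this.

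The nonclinical background makes it relevant. Section 5.2.3.4 reports that hERG and CiPA screening data led to two dog cardiovascular studies, in which QTc rose. The rise stayed below the 10% threshold of concern and was judged not clinically significant, and the 28-day follow-up dog study showed no ECG effects. That is a weak signal, but this is the first human exposure.

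There is also a knock-on effect. Section 7.4 ends treatment when a subject needs a therapy that the study prohibits. Because Torsade-risk drugs are not listed as prohibited, starting one triggers neither that rule nor an ECG. At stake is subject safety; sample size and error rates are not affected.

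**Working it through.** The plan states no figure on this point. The check sets the texts side by side and then counts the scheduled ECGs.

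**Step 1. Does any supplied text restrict starting a Torsade-risk drug after the first dose?**

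| Text | Applies after first dose? | Reaches Torsade-risk drugs as a class? |
|---|---|---|
| Exclusion 14 | No; Section 8 stops at first dose | Yes |
| Exclusion 8 | Yes, stated for the whole of participation | No; only CYP3A4 and P-gp modulators and acid reducers |
| Section 9.3 | Yes, but waived if clinically indicated | No; concerns interference with study treatment |
| Table 12 | Yes, to the last dose | No QT or Torsade row |
| Section 7.5.2 retreatment criteria | Yes, from Cycle 2 | No; co-medication not mentioned |
| Section 7.5.3 | Yes, after a confirmed exceedance | Review only, not a limit on starting |

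No row has a restriction that both continues on study and covers the class. Individual drugs are caught where they are also CYP3A4 or P-gp modulators or fall in another Table 12 row.

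**Step 2. Could Appendix 6 close the gap?** It was not supplied. Table 12 refers to it for herbal products, CYP3A4 and P-gp. The three drug tables in the protocol's List of Tables after the response criteria are CYP3A4 inhibitors, CYP3A4 inducers, and P-gp inhibitors or inducers. A rule in its prose cannot be excluded, but nothing supplied points to one.

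**Step 3. How often would a scheduled ECG be taken?** Inputs are Tables 9 and 10, Table 8 footnote e and Section 13.1.7. Each timepoint is one triplicate set.

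- Escalation, Cycle 1: Day 1 has 6, Day 2 has 1, Days 8, 15 and 22 have 2 each. 6 + 1 + 2 + 2 + 2 = 13.
- Escalation, Cycle 2: Day 1 has 6, Day 2 has 1, Days 8 and 15 have 2 each. 6 + 1 + 2 + 2 = 11.
- Escalation total, Cycles 1 and 2: 13 + 11 = 24 timepoints on 9 days in 56 days.
- Expansion, Cycles 1 and 2 (Table 10): 7 + 7 = 14 timepoints on 4 days in 56 days.
- From Cycle 3, both parts: pre-dose and 2 hours on Day 1 of odd cycles, so 2 timepoints on 1 day per two cycles (2 × 28 = 56 days), plus end of treatment.

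Ratios: 24 / 2 = 12-fold fewer in escalation and 14 / 2 = 7-fold fewer in expansion.

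Gap between ECG days: Cycle 3 Day 1 is study day 57 and Cycle 5 Day 1 is study day 113, so 113 − 57 = 56 days. A drug started on day 58 would first meet a scheduled ECG 113 − 58 = 55 days later, ignoring visit windows.

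**Step 4. Combine.** Section 7.5.3 needs an observed prolongation before it acts. With no prompt for an ECG when a Torsade-risk drug is started, that observation may wait up to about eight weeks in later cycles.

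**The case against.** The strongest case for the plan is that monitoring with reactive management, in place of a class ban, is defensible when the dog QTc change was below the threshold of concern. Several safeguards are real:
- The on-study CYP3A4 restriction is itself part of QT control; Section 7.5.3 names CYP3A4 inhibitors as a route to exposure-related prolongation.
- Potassium and magnesium are in the chemistry panel, which continues on Day 1 of every later cycle.
- Concomitant medication is recorded throughout.
- The investigator is to review ECGs within 24 hours, and a central reader also reads them.
- Section 7.5.3 already calls for co-medication review at each confirmed exceedance, and the Safety Review Committee monitors all toxicity under Section 7.5.4.

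All of this stands and limits the size of the point. None of it restricts starting a Torsade-risk drug or prompts an ECG when one is started.

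Four stronger readings are tempting but not supported:
- A reader might infer that every Torsade-risk drug is freely allowed on study. Those that are also restricted CYP3A4 or P-gp modulators, or fall in another Table 12 class, are not.
- A reader might infer from the 1.2- to 2.5-fold margin in Section 5.2.3.4 that 200 or 300 mg reaches the exposure at which dog effects began. That range belongs to one dog dose level, 50 mg/kg. It rests on concentrations taken from another study and on a predicted human exposure, so it does not show that onset is reached.
- A reader might infer that dose finding is compromised because a mixed-cause QTcF event could count as a dose-limiting toxicity. Counting it is the conservative choice, and the Safety Review Committee reviews it.
- A reader might infer from the Table 8 grid that the ECG schedule is undetermined. Footnote e sits on the ECG row, sends Cycles 1 and 2 to Tables 9 and 10 and sets odd cycles thereafter. Section 13.1.7 agrees on the odd cycles.

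**Conclusion.** The point holds as a gap in on-study medication rules and is worth a cheap correction. As supplied, the plan lets a subject on treatment start a drug from a class the sponsor bars at entry, provided no other restriction catches it, and it asks for no ECG at that time. The reactive rule in Section 7.5.3 depends on an ECG schedule that falls to one day per 56 days from Cycle 3.

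The size in subjects or events cannot be derived; the documents give neither the rate of Torsade-risk co-medication nor the QTcF event rate. The conclusion assumes that Appendix 6 holds no further rule, which its table titles suggest but do not prove.

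Reach is limited. SAP Section 1 says the study was terminated during escalation, and SAP Section 6.2 lists only 100, 200 and 300 mg as conducted. The change therefore matters mainly for re-use of this protocol.

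**What to change.** Add one row to Table 12: drugs known to increase Torsade de Pointes risk, as in exclusion 14, are not to be taken until after the last dose of EZM0414. Allow clinically necessary exceptions agreed with the Medical Monitor, each with an ECG after the drug is started. If Appendix 6 already contains such a rule, a cross-reference from Table 12 and the ECG requirement would be enough.

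The cost is one table row, one ECG per exception and a short Medical Monitor exchange. The downside is some limit on supportive drugs during treatment, which the exception route eases.
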